Number of Participants:	
16 participants randomized 1:1 to immediate start or delayed start intervention
 
Stratification will be performed to divide the number of patients with no to mild fatigue (0-3 numeric rating scale) from patients with moderate to severe fatigue (4-10) because it is possible that the intervention effect is variable depending on baseline level of fatigue.

Study Duration:	Each participant's participation will last up to 6 months.
Study Phases:	Screening for eligibility and obtaining consent
Screening	
Study Treatment	
The exercise coaching program will consist of weekly check-ins for 10 weeks with a certified exercise coach with expertise in caring for oncology patients with a goal of increasing activity to 150 minutes of moderate activity per week. This will be accomplished by shaping behavior through personalized recommendations. Women randomized to the immediate start group will start the intervention during the first week of radiation therapy and continue through and post-completion of radiation. Women randomized to the delayed start group will start the intervention at 6-8 weeks post-radiation.

Follow-Up	Steps, active minutes, patient-reported fatigue, bowel/urinary toxicity, QoL, cognitive function, sexual function and satisfaction, and self-efficacy, as well as distance walked during 6MWT.

Efficacy Evaluations:	
Steps, active minutes, and heart rate measured by a Fitbit device
 
PROMIS Short Form v1.0 – Fatigue 13a (FACT-Fatigue)
 
EPIC Prostate Bowel and Bladder assessment (short form)
 
PROMIS-29 Profile v2.1 QoL (physical function, anxiety, depression, sleep disturbance, pain interference/intensity, ability to participate in social roles and activities)
 
PROMIS Short Form v2.0 – Cognitive Function 4a
 
PROMIS Sexual Function and Satisfaction v2.0 Brief Profile (Female)
 
PROMIS Short Form v1.0 – Self-Efficacy for Chronic Conditions – Managing Daily Activities 4a and Managing Symptoms 4a
 
6MWT

Safety Evaluations:	
Patients can communicate any concerns or safety issues during their weekly check-ins with the exercise coach. They will also be provided with information for contacting an on-call doctor as part of usual care to report any concerning symptoms should they occur outside of the standard evaluation schedule.

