PROMIS Brief Profile Sexual Function and Satisfaction										X		X
Pelvic radiation therapy with IMRT				X	X	X	X	X				
Satisfaction survey												X
Recorded semi-structured exit interview with study PI												X
Early-Intervention Group												
Weekly exercise coach check-ins start x 10 weeks				X (Patients start first check-in during first 5 fractions of RT and continue for a total of 10 weekly sessions. With this schedule, the final session will be post-pelvic RT completion)								
5-10 minute bi-weekly Fitbit check-in call											X (Once every 2 weeks, starting the week after coaching sessions complete for 10 weeks (total 5 calls)).	
Delayed-Intervention Group												
Weekly exercise coach check-ins start x 10 weeks											X (Patients start first check-in after 5-7-week post RT follow-up)	

(Continued) TABLE 1: SCHEDULE OF STUDY PROCEDURES

Study Phase	Screening	Enrollment ¹	RT Simulation	Radiation					Post-Radiation		
Week Number	0		1	(Fraction 1-5)	(Fraction 6-10)	(Fraction 11-15)	(Fraction 16-20)	(Fraction 21-25)	5-7 weeks post RT follow-up ²	6-8 weeks post RT	16-19 weeks post RT follow-up ³
											up, starting 6-8 weeks post RT, and continue for a total of 10 sessions)
5-10 minute bi-weekly Fitbit check-in call				X (Once every 2 weeks starting the first week of RT for a total of 10 weeks (total 5 calls)							

¹Enrollment would occur any time within 7days (before or after) simulation, prior to the start of radiation.

²5-7 week post RT follow-up intended to be soon after completion of intervention in the early-intervention group and before intervention in the delayed-intervention group for purposes of assessment.

³16-19 week post RT follow-up intended to be soon after completion of intervention in the delayed-intervention group for purposes of assessment collection.

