9.3.1.1 Height and weight

9.3.1.2 Patient-reported demographics/medical history (comorbidities)

- Stages of change metric

- All patients will be provided with a Fitbit device and provided detailed instructions on its use (Appendix 7). Data monitoring will start with the time that the Fitbit is provided to the patient after consents are signed and will continue to the end of study enrollment.

- The following baseline assessments are collected:

- FACIT-F
 - EPIC Bowel and Urinary short form assessments
 - PROMIS-29 QoL Metric
 - PROMIS Cognitive Function
 - PROMIS Self-Efficacy for Chronic Conditions
 - 6MWT

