9.3.4 Week 5 of pelvic RT (Fraction 21-25)

Items to be completed at week 5 of RT:

- Fitbit data will be collected on all patients.
- The following assessments are collected:

- FACIT-F
- EPIC Bowel and Urinary short form assessments
- PROMIS-29 QoL metric
- PROMIS Cognitive Function
- PROMIS Self-Efficacy for Chronic Conditions
- 6MWT

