9.3.5 Week 5-7 Post-pelvic RT

Items to be completed at week 5-7 post RT:

- Fitbit data will be collected on all patients.
- The following assessments are collected:
 - FACIT-F
 - EPIC Bowel and Urinary short form assessments
 - PROMIS-29 QoL metric
 - PROMIS Cognitive Function
 - PROMIS Self-Efficacy for Chronic Conditions
 - 6MWT
 - PROMIS Brief Profile Sexual Function and Satisfaction (Female)

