12. DATA ANALYTICS

12.1 Study Objectives

Primary:

The primary objective of this study is to evaluate the feasibility of conducting a randomized trial of an exercise coaching program to encourage physical activity for women treated with adjuvant pelvic intensity-modulated radiation therapy treatment for endometrial cancer.

Secondary:

- 1) To collect initial efficacy evaluation of the exercise coaching program on patient-reported fatigue, bowel/urinary toxicity, QoL, cognitive function, sexual function and satisfaction, and self-efficacy, as well as distance walked during 6MWT between the immediate and delayed-start group from baseline to pre-specified time points (end of RT, 5-7 weeks post RT, and 16-19 weeks post RT) to guide statistical planning for follow-up study.
- 2) To measure the prevalence of fatigue at baseline in the population of endometrial cancer patients recommended pelvic radiation therapy using data collected in the screening process.
- 3) To explore potential behavioral mechanisms (mediators) and variables that influence the strength of the intervention effect (moderators).

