 - a. Individual adherence to the physical activity monitor will be defined as wearing the activity tracker for at least 8 hours a day for 70% of the days in the study. Heart rate will be used to determine wear-time. We set an a priori goal of overall 70% participant adherence to the physical activity monitor, to be analyzed per cohort (6 of 8 participants in each arm demonstrating adherence as defined above).
- 5) Adherence to recommendation of 150 minutes per week of moderate physical activity:
 - a. Individual adherence to regular physical activity will be defined as meeting the recommendation of 150 minutes of moderate physical activity per week, based on the Physical Activity Guidelines for Americans developed by the U.S. Department of Health and Human Services (HHS). The target for participant adherence is set at an a priori goal of 70%.

The *resource and management* feasibility will be assessed based on the capacity of the exercise coach and research team to perform the required tasks of the protocol:

- 1) Adherence to the timeline of study procedures and human and data management issues that could potentially arise during a full-scale RCT will be tracked. Adherence to the study timeline for completion of required patient surveys and 6MWT as well as appropriate scheduling (patient attendance not required) of the exercise coaching sessions and follow-ups will be a proxy measurement of research resource and human data management acceptability. We set an a priori goal of 80% adherence.

Secondary Objective Analytical Plan

- 1) Changes in patient-reported fatigue, bowel/urinary toxicity, QoL, cognitive function, sexual function and satisfaction, and self-efficacy, as well as distance walked during 6MWT from baseline to pre-specified time points (end of RT, 5-7 weeks post RT, and 16-19 weeks post RT) within and between each group will be compared using two-sample t-test or Wilcoxon Rank Sum test when appropriate. Repeated measure models/linear mixed effect models may also be used to explore the changes in self-reported questionnaires over time among different treatment groups. Data will be analyzed based on the intention-to-treat principle and used to estimate treatment effect size for future trial design.
- 2) Prevalence of fatigue at baseline in the population of endometrial cancer patients receiving pelvic radiation therapy will be reported using data collected in the screening process.

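### Sexual function is to be analysed as change from baseline at three time points, but its questionnaire is never given at baseline or at the end of RT, so none of the three changes can be computed

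*Protocol*

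**What the plan says.** **Analysis text.** Secondary objective 1 (Protocol 12.1, also 2.1 and the synopsis) evaluates a list of outcomes, sexual function among them, "between the immediate and delayed-start group from baseline to pre-specified time points". Section 12.2 makes this an analysis of changes, within and between groups, in a list that includes "sexual function and satisfaction, and self-efficacy, as well as distance walked during 6MWT from baseline to pre-specified time points". The time points are end of RT, 5-7 weeks post RT and 16-19 weeks post RT. The methods are a two-sample t-test or Wilcoxon rank sum test, with repeated-measures or mixed models as an option. The results are to be "used to estimate treatment effect size for future trial design".

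**Schedule.** Under Enrollment (9.3.1), the list headed "The following baseline assessments are collected" names FACIT-F, EPIC bowel and urinary, PROMIS-29, PROMIS Cognitive Function, PROMIS Self-Efficacy and the 6MWT. Section 9.3.4, headed "Items to be completed at week 5 of RT", names the same six. The "PROMIS Brief Profile Sexual Function and Satisfaction" questionnaire is added only in 9.3.5 (5-7 weeks post RT) and 9.3.6 (16-19 weeks post RT). Its row in Table 1 carries two marks, where each of the other six measures carries four.

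**The concern.** A change from baseline needs a baseline. For sexual function the protocol plans the change but does not schedule the measurement, and it does not say whether the schedule or the analysis text is the intended version.

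Three things are lost for this outcome if nothing is done:

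- The planned change-from-baseline comparison cannot be run.
- The follow-up trial gets no effect size, SD of change or baseline/follow-up correlation from the pilot.
- The immediate arm's own change over its coaching cannot be seen. Ten weekly sessions starting in the first of five RT weeks end about 5 weeks after RT, and footnote 2 of Table 1 places the 5-7 week visit soon after that. The first measurement therefore comes at or after the end of coaching.

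A baseline missed before RT cannot be collected later for that participant.

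**Working it through.** The protocol gives no figure to reproduce here. The check sets the planned analysis beside the schedule.

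**Step 1: what is collected when** (9.3.1, 9.3.4, 9.3.5, 9.3.6; Table 1 agrees).

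| Measure | Enrollment | Week 5 of RT | 5-7 wk post RT | 16-19 wk post RT |
|---|---|---|---|---|
| FACIT-F, EPIC, PROMIS-29, Cognitive Function, Self-Efficacy, 6MWT (six measures) | yes | yes | yes | yes |
| Sexual function and satisfaction | no | no | yes | yes |

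Sexual function is the only one of seven measures given at 2 of 4 visits.

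**Step 2: which changes can be computed.** A change to time t needs a value at baseline and a value at t.

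| Planned change, sexual function | Baseline value | Value at t | Computable |
|---|---|---|---|
| Baseline to end of RT | missing | missing | no |
| Baseline to 5-7 weeks post RT | missing | present | no |
| Baseline to 16-19 weeks post RT | missing | present | no |

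That is 0 of 3. Adding the questionnaire at enrollment gives 2 of 3; adding it at week 5 of RT as well gives 3 of 3.

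**Step 3: is there another source of a baseline?** The synopsis (Efficacy Evaluations) describes EPIC as bowel and bladder only. It lists the PROMIS-29 domains as "physical function, anxiety, depression, sleep disturbance, pain interference/intensity, ability to participate in social roles and activities". Neither covers sexual function.

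**Step 4: what the schedule still supports.**

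- A between-arm comparison of scores at 5-7 weeks, unbiased because allocation is randomised.
- The delayed arm's change from 5-7 to 16-19 weeks, intended to span its coaching.
- The between-arm comparison of that change.

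**Step 5: precision with and without a baseline.** This takes 8 per arm, all 16 providing data, and equal SDs at both visits. The baseline/follow-up correlation r is an assumption, because the protocol gives none. Standard errors of the between-arm difference at 5-7 weeks, in SD units:

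- Levels: √(1/8 + 1/8) = 0.50
- Simple change: 0.50 × √(2(1 − r))
- Baseline-adjusted, large-sample: 0.50 × √(1 − r²)
- Baseline-adjusted with the small-sample factor √(1 + 1/(2n − 4)) = √(1 + 1/12) = 1.04 for n = 8 per arm

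| Assumed r | Levels (as scheduled) | Simple change | Baseline-adjusted | Baseline-adjusted, small-sample |
|---|---|---|---|---|
| 0.3 | 0.50 | 0.59 | 0.48 | 0.50 |
| 0.5 | 0.50 | 0.50 | 0.43 | 0.45 |
| 0.7 | 0.50 | 0.39 | 0.36 | 0.37 |

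The loss of precision from having no baseline runs from none to moderate.

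**The case against.** The contradiction itself cannot be rebutted: the visit lists and Table 1 agree with each other, which rules out a garbled table, and a separate SAP cannot supply a measurement that is not scheduled. The case on the other side concerns how much it matters.

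- **The optional mixed model could be run on the two scheduled visits.** True, but it would describe change between two post-RT visits. It cannot give change from an unmeasured baseline.
- **Little precision is lost.** Largely right for the method the protocol names. With simple change, having a baseline is worse than comparing levels at r = 0.3, equal at r = 0.5 and better only at r = 0.7. The case for correction rests on a planned analysis that cannot be carried out, and precision is secondary.
- **The schedule may be deliberate, and the analysis text just a collective list.** Possible, since the questionnaire is consistently absent before 5-7 weeks. The protocol gives no reason, however, and the analysis text would then still need correcting wherever it appears.
- **The comparisons that remain need care.** This stands. If the delayed arm starts coaching in week 8, its tenth weekly session falls in week 17, while the last visit may be in week 16. The between-arm comparison of the 5-7 to 16-19 week change starts after the immediate arm's coaching. It therefore mixes the delayed arm's response with the persistence or fading of the immediate arm's effect. Only the 5-7 week comparison of levels contrasts coached with not-yet-coached participants.
- **It is one secondary outcome in a 16-patient pilot with a feasibility aim.** Agreed. This limits the severity but does not remove the contradiction.

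**Conclusion.** The point holds and should be fixed. The analysis stated for sexual function cannot be carried out on the stated schedule: 0 of 3 changes from baseline are computable, against 3 of 3 for each of the other six measures. This follows from the protocol's own visit lists and table and rests on no assumption. Only the precision figures depend on assumed correlations and complete data.

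The damage is confined to one secondary outcome. A between-arm effect size at 5-7 weeks can still be estimated, with a standard error of 0.50 SD if all 16 participants give data.

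**What to change.** Decide which text is intended and bring the other into line before the first participant starts RT.

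**Option (a): change the schedule.** Add the sexual function questionnaire at enrollment and at week 5 of RT in 9.3.1, 9.3.4 and Table 1. If only one visit can be added, it should be enrollment; the end-of-RT change for this outcome must then be dropped from the analysis text. The cost is a brief questionnaire in one or two surveys already being given, with slight respondent burden.

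**Option (b): change the analysis text.** Keep the schedule and take sexual function out of the change-from-baseline wording in the synopsis, 2.1, 12.1 and 12.2. Specify instead:

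- the between-arm comparison of scores at 5-7 weeks post RT, as the main comparison for this outcome;
- the 5-7 to 16-19 week change by arm and compared between arms, described as exploratory, stating that the immediate arm's starting value is post-coaching and that the last visit may precede the delayed arm's final session.

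This costs only wording, but gives up change from baseline for this outcome.

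If enrollment has already begun, option (a) helps only participants who have not yet started RT, and the text should say how those without a baseline will be handled.

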	
track steps and active minutes:
 
 a. Individual adherence to the physical activity monitor will be defined as wearing the activity tracker for at least 8 hours a day for 70% of the days in the study. Heart rate will be used to determine wear-time. We set an a priori goal of overall 70% participant adherence to the physical activity monitor, to be analyzed per cohort (6 of 8 participants in each arm demonstrating adherence as defined above). 5. Adherence to recommendation of 150 minutes per week of moderate physical activity: 
 a. Individual adherence to regular physical activity will be defined as meeting the recommendation of 150 minutes of moderate physical activity per week, based on the Physical Activity Guidelines for Americans developed by the U.S. Department of Health and Human Services (HHS). The target for participant adherence is set at an a priori goal of 70%. 
The resource and management feasibility will be assessed based on the capacity of the exercise coach and research team to perform the required tasks of the protocol:
 
 1. Adherence to the timeline of study procedures and human and data management issues that could potentially arise during a full-scale RCT will be tracked. Adherence to the study timeline for completion of required patient surveys and 6MWT as well as appropriate scheduling (patient attendance not required) of the exercise coaching sessions and follow-ups will be a proxy measurement of research resource and human data management acceptability. We set an a priori goal of 80% adherence. 
Secondary Objective Analytical Plan
 
 1. Changes in patient-reported fatigue, bowel/urinary toxicity, QoL, cognitive function, sexual function and satisfaction, and self-efficacy, as well as distance walked during 6MWT from baseline to pre-specified time points (end of RT, 5-7 weeks post RT, and 16-19 weeks post RT) within and between each group will be
--	---

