	
compared using two-sample t-test or Wilcoxon Rank Sum test when appropriate. Repeated measure models/linear mixed effect models may also be used to explore the changes in self-reported questionnaires over time among different treatment groups. Data will be analyzed based on the intention-to-treat principle and used to estimate treatment effect size for future trial design.
 
 2. Prevalence of fatigue at baseline in the population of endometrial cancer patients receiving pelvic radiation therapy will be reported using data collected in the screening process. 3. Exploratory analysis of potential behavioral mechanisms (mediators) and variables that influence the strength of the intervention effect (moderators) will be performed.
Data and Safety Monitoring Plan:	Internal quality assurance team will be responsible for monitoring the safety and data acquisition for this study.

TABLE OF CONTENTS

SUMMARY OF CHANGES	2
ABSTRACT.....	3
ABBREVIATIONS AND DEFINITIONS.....	5
PROTOCOL SYNOPSIS	6
TABLE OF CONTENTS.....	14
TABLE 1: SCHEDULE OF STUDY PROCEDURES	17
1. BACKGROUND	20
1.1 Study Disease(s) or Condition(s)	20
1.2 Product(s) / Agent(s)	20
1.3 Rationale.....	20
1.4 Relevant Literature and Data.....	22
1.5 Compliance Statement.....	24
1. 24	
2. OBJECTIVES.....	24
Primary Objective	24
2.1 Secondary Objective	24
3. SETTINGS	25
3.1 Study Sites.....	25
3.2 Community Involvement.....	25
3.3 Outside of Organization	25
4. RESOURCES AVAILABLE	25
4.1 Conducting Research.....	25
4.2 Medical Resources	26
5. INVESTIGATIONAL PLAN.....	26
5.1 General Schema of Study Design.....	26
5.2 Product(s) / Agent(s)	27
5.3 Allocation to Treatment Groups and Blinding/Randomization	27
6. STUDY TIMELINE	27
6.1 Individual Participation.....	27
6.2 Study Timeline	27
7. PARTICIPANT SELECTION	28

7.1	Eligibility Criteria	28
8.	RECRUITMENT METHODS	28
8.1	Methods.....	28
8.2	Materials.....	29
9.	STUDY PROCEDURES.....	29
9.1	Screening Visit	29
9.2	Participant Survey of Patient-Reported Outcomes and Information.....	29
9.3	Study Intervention Visits.....	30
9.4	Unscheduled Visits.....	32
9.5	Non-compliance and Lost to Follow-Up.....	32
10.	STUDY ADMINISTRATION	33
10.1	Study Intervention(s) Administration.....	33
10.2	Measures to Minimize Bias: Randomization / Blinding	34
11.	DATA COLLECTION AND MANAGEMENT	34
11.1	Data Collection and Management	34
11.2	Security	35
11.3	Release of Locally Banked Data	36
11.4	Confidentiality	36
12.	DATA ANALYTICS	37

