5. INVESTIGATIONAL PLAN

5.1 General Schema of Study Design

This is a pilot feasibility study using a randomization of immediate versus delayed intervention.

See Table 1: Schedule of Study Procedures.

- 5.1.1 Hypothesis: This is a pilot study, so there is no hypothesis. However, we have set a priori criteria for evaluating the primary outcomes of the study. This study will explore the feasibility of conducting a randomized trial of an exercise coaching program to encourage physical activity for women undergoing adjuvant pelvic intensity-modulated radiation therapy treatment for endometrial cancer to guide the design of future studies to investigate the effect of exercise to treat or mitigate fatigue, to identify successful strategies for improving adherence to exercise, and to understand which population of patients may benefit most from a targeted program to increase motivation and overcome barriers to exercise.

- 5.1.2 Study Design: A total of 16 women treated with radical or modified radical hysterectomy for Stage I-IVA endometrial cancer who are planned to complete pelvic external beam radiation therapy as part of their adjuvant treatment will be included. Patients will be randomized to either an immediate- or delayed-start of their exercise coaching program. Women randomized to the immediate-start group will start the intervention during the first week of radiation therapy and continue through and post-completion of radiation. Women randomized to the delayed-start group will start the intervention at 6-8 weeks post-radiation, a more typical period in survivorship where exercise counseling may begin. Participants will be asked to wear an activity monitor to track steps and moderate activity minutes and to complete assessments of patient-reported cancer-related fatigue, bowel/urinary toxicity, sexual health, and quality of life and participate in a six-minute walk test (6MWT) at predefined time points throughout the study.

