12.2 Analytics

This study will enroll 16 patients. At the Inova Schar Cancer Institute Fairfax location, approximately 24 patients will undergo a course of pelvic radiation per year. Additionally, approximately 24 patients will undergo a course of pelvic radiation per year across Inova Loudoun, Inova Alexandria, and Inova Fair Oaks Hospitals. With the goal of the study to evaluate adherence to and the acceptability and feasibility of the intervention as part of a pilot study, the sample size was determined with the goal of completing accrual of the study within one year, accruing across all four sites.

Primary Objective Analytical Plan

Feasibility of conducting a randomized trial of this nature will be evaluated on the basis of process feasibility and resources and data-management feasibility.

The *process* feasibility will be evaluated on:

- 1) Recruitment acceptability from the provider and patient perspective:
 - a. Provider acceptability of the intervention will be defined as the proportion of patients identified on pre-screening by the PI that the primary clinician agrees of patient suitability for offering enrollment on the trial and proceeding to completion of screening steps if patient is interested in the study. We set an a priori goal of 50% provider acceptability.
 - b. Patient acceptability of the intervention will be defined as the proportion

of patients who agreed to consent and then proceed to completion of screening steps. We set an a priori goal of 50% patient acceptability.

- 2) Appropriateness of the screening criteria:
 - a. Screening criteria appropriateness will be defined as the proportion of patients who are screened who proceeded to allocation of intervention groups. We set an a priori goal of 50% of appropriateness of the screening criteria.
- 3) Adherence to the exercise coaching session intervention:
 - a. Individual adherence to coaching sessions will be defined as complete adherence when engaging in 10 of the 10 planned exercise coaching sessions and high adherence as engaging in at least 7 of the planned 10 exercise coach check-ins. We set an a priori goal of overall 70% participant adherence to the coaching sessions, to be analyzed per cohort (6 of 8 participants in each arm demonstrating high adherence as defined above).
- 4) Adherence to the physical activity monitor usage to track steps and active minutes:

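### Sexual function is promised as change from baseline but is never measured at baseline, and within-arm change is assigned only unpaired tests (the second defect is minor)

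*Protocol*

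**What the plan says.** Item 1 of the Secondary Objective Analytical Plan (section 12.2) covers fatigue, bowel and urinary toxicity, quality of life, cognitive function, sexual function and satisfaction, self-efficacy and the 6MWT. Changes from baseline to three later time points "within and between each group will be compared using two-sample t-test or Wilcoxon Rank Sum test when appropriate". The synopsis has the same sentence, split across a page break: "within and between each group will be" and then "compared using two-sample t-test or Wilcoxon Rank Sum test when appropriate". Secondary objective 1 (synopsis, section 2.1, section 12.1) lists the same outcomes from baseline to the same time points, but asks only for the comparison between the arms.

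The next sentence of section 12.2 adds an option: "Repeated measure models/linear mixed effect models may also be used to explore the changes in self-reported questionnaires over time". Section 5.1.1 states: "This is a pilot study, so there is no hypothesis".

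The assessment lists are separate. Section 9.3.1 opens its list with "The following baseline assessments are collected", and section 9.3.4 opens its own with "Items to be completed at week 5 of RT". Neither list contains the sexual function questionnaire. It appears in sections 9.3.5 (5-7 weeks post RT) and 9.3.6 (16-19 weeks post RT).

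**The concern.** The two problems sit in the same analysis sentence.

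**(a) Sexual function.** A change from baseline needs a baseline value, and a change to end of RT also needs an end-of-RT value. The schedule collects neither. A named secondary outcome, meant to help plan the follow-up study, therefore cannot be analysed as written in either arm. A pre-radiation value cannot be obtained once a woman has started RT.

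**(b) Within-arm tests.** The two-sample t-test and the rank-sum test assume independent samples. Between arms, applied to change scores, that is right. Within an arm, baseline and follow-up come from the same women, and the protocol names no paired t-test, signed-rank test or one-sample test on the changes. At stake is the precision of exploratory within-arm results, most plainly for the 6MWT, which the optional models do not reach.

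**Working it through.** **(a) Promise against schedule.** No arithmetic assumption is needed.

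| Time point | Role in the analysis plan | Sexual function collected? |
|---|---|---|
| Enrollment | baseline for every change | No (9.3.1) |
| Week 5 of RT | change to end of RT | No (9.3.4) |
| 5-7 weeks post RT | change to this visit | Yes (9.3.5) |
| 16-19 weeks post RT | change to this visit | Yes (9.3.6) |

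Table 1 agrees with the text: the sexual function row carries two marks, while the fatigue, bowel/urinary, PROMIS-29, cognitive function, self-efficacy and 6MWT rows carry four. The gap is therefore not an artefact of how the table was read. Each promised change is value(t) minus value(baseline). The baseline term is missing by design, so none of the three can be computed. Two quantities remain available: the values at the two post-RT visits, and the within-woman change between those visits.

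**(b) Size of the test mismatch.** The protocol states no alpha, SD, effect size or within-person correlation (rho), so there is no figure of its own to reproduce.

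Inputs:
- n = 8 per arm, from section 12.2 ("6 of 8 participants in each arm demonstrating high adherence as defined above").
- Assumed: two-sided 5%, normal data, equal SDs at both times, a true change of 0.8 SD, rho from 0 to 0.7.

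Formulas, in SD units:
- True SE of the mean change = sqrt(2(1 - rho)/n). The unpaired test works with sqrt(2/n), too large by the factor 1/sqrt(1 - rho): 1.41 at rho 0.5 and 1.83 at rho 0.7.
- Unpaired t: 14 df, critical value 2.145. Type I error and power by simulation (4,000,000 arms per setting).
- Paired t: 7 df, critical value 2.365. Power from the noncentral t with ncp = 0.8 x sqrt(8)/sqrt(2(1 - rho)). At rho 0.5, ncp = 0.8 x 2.828/1 = 2.26.

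| rho | Unpaired t, type I error | Unpaired t, power | Paired t, power |
|---|---|---|---|
| 0 | 5.0% | 32% | 28% |
| 0.1 | 4.0% | 31% | 31% |
| 0.3 | 2.3% | 30% | 38% |
| 0.5 | 1.1% | 28% | 50% |
| 0.7 | 0.3% | 25% | 71% |

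The rank tests behave alike. At rho 0.5, power is 27% for rank-sum and 43% for signed-rank; the signed-rank test leads only above rho of about 0.2. (Their exact sizes at n = 8 differ slightly, 0.0499 and 0.0391.)

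For 95% intervals, the approximate width ratio, unpaired to paired, is (2.145/2.365)/sqrt(1 - rho): 0.91 at rho 0, 1.28 at 0.5 and 1.66 at 0.7. Break-even is rho = 1 - (2.145/2.365)^2 = 0.18.

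**The case against.** The strongest reply on (b) is that it hardly matters. The study has no hypothesis, the secondary objective asks only for a between-arm comparison, and the stated use of the results is a treatment effect size, which is a between-arm quantity. Mixed models, which handle pairing, are already allowed for the questionnaires, and a statistical analysis plan may spell out the tests. Most of this stands and sets the weight. It does not remove the error. The sentence itself names tests for within-arm change, and both are unpaired. Its closing qualifier most naturally governs the choice between those two tests. The mixed models are optional and omit the 6MWT.

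A reader might go further and infer that within-arm 6MWT change has no valid test, or that the wording could produce false claims of benefit. The figures do not support that: at every non-negative correlation tried, type I error is at or below 5%. The test is inefficient, not error-inflating. At low correlation the paired tests are no better or somewhat weaker.

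On (a), leaving the questionnaire out before and during RT may be deliberate; the protocol does not say. If so, the analysis wording is what must change. Nor is the outcome lost: the arms can still be compared on values at the two visits where it is collected.

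**Conclusion.** Both parts hold, with different weight.

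(a) is a plain contradiction between schedule and analysis and rests on no assumption. Sexual function has no baseline and no end-of-RT value, so none of the three promised changes can be computed. It is confined to one secondary outcome.

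(b) is a wrong statement of method with minor effect. It touches only exploratory within-arm results. Between-arm effect sizes and all feasibility criteria are unaffected by it. The loss is material only at moderate or high within-person correlation (28% against 50% power at 0.5). Those figures depend on the assumed correlation, effect size, alpha and normality. That paired data call for a paired test does not. The conservative direction assumes positive correlation, which is what one expects of repeated measurements on the same woman.

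**What to change.** **(a) Choose one.**

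(i) Wording only, in five places: synopsis secondary objective 1, synopsis analytical plan, and sections 2.1, 12.1 and 12.2. For sexual function, drop the reference to baseline and the end-of-RT time point. Compare the arms on values at 5-7 weeks post RT (which Table 1, footnote 2, places before coaching in the delayed arm) and at 16-19 weeks post RT. Limit any within-arm analysis to the change between those two visits. State that chance baseline imbalance, with 8 per arm, cannot be adjusted for.

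(ii) Add the questionnaire at enrollment (section 9.3.1 and Table 1), and at week 5 of RT (section 9.3.4 and Table 1) if the end-of-RT result is to stay. This costs one or two short questionnaires per woman. Baseline cannot be recovered for any woman already enrolled.

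**(b)** In section 12.2 and the synopsis analytical plan, state: *Within-arm change from baseline, for outcomes measured at baseline, will be analysed by paired t-test or Wilcoxon signed-rank test, reported as mean change with 95% CI; between-arm comparison of changes will use the two-sample t-test or Wilcoxon rank-sum test.* The restriction to outcomes measured at baseline keeps sexual function out of this sentence under option (i). The cost is one sentence in two places and no extra data.
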